1.0 STATISTICAL CONSIDERATIONS

1.1 IVIG + Rituximab for Desensitization

Primary Objective:

This trial is designed to determine if Rituximab + IVIG is effective in improving rates of transplantation for highly-HLA sensitized DD candidates on the UNOS waiting list over a 9M period of time after completion of treatment. Results will be compared to transplant rates in a group of age and anti-HLA antibody matched patients who remain on the UNOS wait list during the study period. This is the PRIMARY END POINT. Secondary end points include and will be evaluated based on time line in appendix A:

Transplantation rate assumptions:

- 60-65% in the IVIG + Rituximab group
- ~15% in the non-desensitized patients on UNOS wait list

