Rates of transplantation for highly-HLA sensitized patients (HS) are exceedingly low (<10% of patients with PRAs > 30% receive DD kidneys each year). IVIG 10% has been demonstrated as an effective desensitization agent in placebo controlled trials (1). However, in this study, only 35% of treated patients vs 17% placebo were able to receive a working kidney transplant, most from DD. Recent uncontrolled data from our group demonstrated a robust effect on improvement of transplant rates for HS patients (80% treated) using a combination of IVIG + rituximab (2,3). This was also associated with improved reductions in donor-specific antibody levels (DSA) and flow-cytometry crossmatches at the time of transplant (4-8). This protocol appeared to be particularly effective in improving rates of transplantation for HS patients awaiting DD transplantation. Our group has also developed novel methodologies to predict the risk of antibody-mediated rejection (ABMR) post-transplant based on DSA and FCMX results after desensitization. This allows us to improve the prediction of acceptable donor-specific antibody (DSA) levels that are permissive for allowing transplantation to go forward (3-8).

With these considerations and observations in mind, we have formulated the following hypothesis. We believe that the addition of the novel B-cell depleting agent (Rituximab) to IVIG treatment will offer significant benefits in reducing anti-HLA (DSA) thus improving rates and outcomes of DD transplantation above that seen for highly-HLA sensitized patients awaiting DD transplant on the UNOS list. In addition, we will assess the ability of Rituximab to lower DSA levels and reduce allograft injury post-transplantation. Protocol biopsies will be performed at time of transplant and at 12M post-transplant to determine the incidence of chronic antibody mediated rejection (Transplant Glomerulopathy {TG}). These biopsies will be read by the pathologist at participating institutions and graded according to Banff Criteria (2005) (9).

TARGET POPULATION:

Patients with end-stage renal disease on dialysis (ESRD, CKD Stage V), ages 18-65 years who are awaiting deceased donor (DD) kidney transplantation on the UNOS wait list have a Panel Reactive Antibody (PRA) >30% and a significant sensitization history (previous pregnancies, blood transfusions and/or previous transplants) with sufficient wait time to allow frequent DD offers with positive crossmatches (CMXs) that prohibit transplantation.

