Figure 5: Pre-Transplant Desensitization Protocol for deceased donor recipients:

[figure not shown]
[figure not shown]

Figure 6 Shows the Post-Transplant Management Protocol for Patients Receiving DD Transplants.

ACCRUAL GOAL: 75 subjects

DURATION OF ACCRUAL: 24 months

DURATION OF FOLLOW-UP: 9 months for all desensitized subjects, 12 months for all transplanted subjects

THERAPY STOPPING RULES: Safety stopping rules for the study include:

The study will be put on hold and re-evaluated for safety signals if significant adverse events (serious infusion reactions, serious infections or death and or graft loss from early ABMR) are seen in three of the first 5 patients. In addition, if biopsy proven ABMR is seen in 4 of the first 10 patients entered, the study will be stopped for re-evaluation.

Efficacy Stopping Rules:

The DSMB will review cumulative safety and efficacy data according to a pre-specified schedule, not less frequently than quarterly. Based on these data (after the pre-specified data reviews, the DSMB may recommend alterations or stopping of the protocol.

CONCOMITANT MEDICATIONS: Concomitant therapy will include a standard immunosuppressive regimen of mycophenolate mofetil (CellCept[®]) at 1200 mg/m²/day given in two divided doses, Tacrolimus (Prograf[®]) given at 0.05 to 0.15 mg/kg divided twice daily, and prednisone loading dose and taper as per center protocol. Induction therapy using Campath 1H 30mg SQ/IV at the time of transplant OR Thymoglobulin[®] (total dose not to exceed 6.0mg/kg) IV per center protocol will be given to subjects on study. The safety and efficacy of Campath 1H induction therapy after desensitization with IVIG + Rituximab has been previously described for adults (11,12).

Therapy for recurrent biopsy proven rejection will be initiated as standard of care at participating institutions. The recommended initial rejection therapy will consist of pulse Solumedrol per center protocol. Alternatively, Thymoglobulin will typically be given for 5-10 days, depending on the time of return of creatinine levels to baseline. If resistant ABMR is seen, the use of IVIG +Rituximab (anti-CD20 monoclonal antibody) and/or plasmapheresis will be considered. In addition, the use of monoclonal antibodies to the complement component C5 (Eculizumab[®], Alexion, Cheshire, CT) may be used at the discretion of the investigators.

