1.3.3 Methods of Analysis

Rituximab + IVIG for Desensitization

We aim to recruit 75 HS patients on the basis of a clinically relevant increase in the absolute rate of transplantation for highly-HLA sensitized deceased donor recipients of approximately 50 percentage points between the two groups during 9 months of follow-up, with an estimated event rate of 15% in the control UNOS study group. We determined that this number of patients would provide the study with a power of 95%, with a two-sided type I error of 5% and a nonadherence or loss to follow up rate of 5(or 10)%. A transplant rate of 60-70% in the intervention limb is based on our experience with desensitization in the recent years (49, 113, 131). All analyses shall be performed on the basis of the intention-to-treat principle. Patients that were transplanted outside of the study will be included in the analysis.

We shall compare the proportions of patients in the treatment group compared to the UNOS control group using time-to-event analysis with respect to outcomes such as the primary outcome (rate of transplantation) and certain secondary outcomes (such as recipient and graft survival, occurrence of rejection in the treatment group only). These outcomes shall be analyzed with the use of the log-rank test. Cox proportional-hazards regression shall be used to obtain unadjusted hazard ratios and to adjust for significant stratifying variables and to test for effect modification in all secondary analyses. Data from patients who are lost to follow-up shall be regarded as censored at the time of the last contact. Data from patients who do not receive transplantation shall be censored at end of 9 months post desensitization. We shall use Kaplan–Meier estimates of the proportion of patients with the above listed outcomes. We shall calculate the number of patients who would need to be desensitized to allow one deceased donor renal transplant from the hazard ratio and its 95% confidence interval.

For other outcomes, the Chi square or Fischer exact test shall be used if the variable is categorical, and the t-test or signed rank test if it is continuous variable.

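### The concurrent UNOS control group is not matched or adjusted on waiting time, is defined by later list status, and has no time zero or usable censoring rule

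*Combined protocol and SAP*

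**What the plan says.** Section 1.1 of the statistical considerations makes transplantation within 9 months of completing treatment the primary end point. The comparator is "a group of age and anti-HLA antibody matched patients who remain on the UNOS wait list during the study period". The assumed rates are 60-65% in treated patients and about "15% in the non-desensitized patients on UNOS wait list".

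Section 1.3.3 plans a difference of about 50 percentage points between the two groups during 9 months of follow-up, "with an estimated event rate of 15% in the control UNOS study group". The groups are to be compared by log-rank test, Cox regression and Kaplan-Meier estimates. Cox regression is also "to adjust for significant stratifying variables", which are not listed. The only stratifier named is PRA above or below 80%, for a subgroup analysis.

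On follow-up, the same section says: "Data from patients who do not receive transplantation shall be censored at end of 9 months post desensitization". Patients lost to follow-up are censored at last contact. After the intention-to-treat statement it adds: "Patients that were transplanted outside of the study will be included in the analysis".

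On entry, the Target Population paragraph asks for wait-listed patients "with sufficient wait time to allow frequent DD offers with positive crossmatches (CMXs) that prohibit transplantation". Recipient inclusion criterion 4 likewise requires enough UNOS waiting time for deceased-donor offers.

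**The concern.** The study is open label and not randomised, and this is its only concurrent control for the transplant rate. The comparison is only as good as the control group's definition, which rests on one sentence.

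**Waiting time.** The protocol itself links waiting time to receiving offers and selects treated patients on it. Controls matched on age and antibody alone may sit at a different point on the list. If so, part of any difference in transplant rate would reflect list position.

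**Selection by later status.** A transplanted patient leaves the list. Choosing controls who *remain* on it conditions on what happens after the comparison should have begun, and conflicts with counting their transplants.

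**Time zero and censoring.** A log-rank or Cox analysis needs a start date and a censoring rule in each group. Treated patients have both. Controls have no stated start date, and they never reach a date defined as months after desensitization. Two analysts could therefore build different control data sets from the same registry.

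**Working it through.** **1. What entry, matching and adjustment each use**

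| Factor | Trial entry | Control matching (1.1) | Named for adjustment or stratification (1.3.3) |
|---|---|---|---|
| Age | yes | yes | no |
| Anti-HLA antibody / PRA | yes | yes | yes, at 80%, as a subgroup |
| Waiting time sufficient for offers | yes | no | no |

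The log-rank test as described is unadjusted. The sentence on Cox adjustment ends by referring to secondary analyses, so it is unclear whether the primary hazard ratio is adjusted at all.

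**2. Evidence that waits were long**

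- Preliminary data: deceased-donor recipients had waited 95 ± 46 months before desensitization (95/12 = 7.9 years). Deceased-donor candidates are described as more than 5 years on the list.
- Section 1.2: patients in the placebo-controlled phase averaged more than 11 years, but on dialysis, which is not list time.

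All these are earlier patients. The supplied text gives no waiting time for controls. Section 1.3.1 describes untreated transplant rates by sensitization level, not by accrued waiting time. Neither size nor direction of bias can be derived.

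**3. Illustration, on an assumption**

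The planned figure reproduces: 65% - 15% = 50 points. At 60% treated it is 45 points, and at the 50% used in section 1.2 it is 35.

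Let treated patients, had they gone untreated, have a transplant hazard *k* times that of the planned controls. The values of *k* are assumed. At constant hazard:

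- like-with-like control rate at 9 months = 1 - 0.85^k
- difference = treated rate - that rate
- hazard ratio = ln(1 - treated rate) / ln(1 - that rate)

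For *k* = 2: 1 - 0.85² = 27.8%; 65 - 27.8 = 37.2 points; ln(0.35)/ln(0.7225) = 3.23.

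| k | Control rate | Difference at 65% / 60% / 50% treated (points) | Hazard ratio at 65% / 60% / 50% |
|---|---|---|---|
| 0.5 | 7.8% | 57.2 / 52.2 / 42.2 | 12.92 / 11.28 / 8.53 |
| 1 (plan) | 15.0% | 50.0 / 45.0 / 35.0 | 6.46 / 5.64 / 4.27 |
| 1.5 | 21.6% | 43.4 / 38.4 / 28.4 | 4.31 / 3.76 / 2.84 |
| 2 | 27.8% | 37.2 / 32.2 / 22.2 | 3.23 / 2.82 / 2.13 |
| 3 | 38.6% | 26.4 / 21.4 / 11.4 | 2.15 / 1.88 / 1.42 |

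The plan would report the *k* = 1 row whichever row were true.

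**4. Time zero**

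The treatment course runs from day 0 to day 30, and the treated clock starts at completion. If the control clock started at the treated patient's day 0 and stopped at the same calendar date, controls would have about 10 months: 1 - 0.85^(10/9) = 16.5% against 15.0%, a shift of 1.5 points in the proportion. At constant hazard the extra month would not move the log-rank or Cox result. A clock started at each control's listing date would matter more: it would put controls at zero accrued waiting time and bring back the imbalance in part 1. The text excludes none of these choices.

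**The case against.** Much of the wording point is answered by the text. The sentence in section 1.1 compares transplant *rates in* the control group, and a 15% rate is assumed twice. A reader might infer that every transplanted control is excluded, leaving no control events and no estimable hazard ratio. The documents do not support that; control transplants are meant to count. What stands is that the selection phrase, applied as a registry filter, contradicts that intent. The sentence on transplants outside the study does not name controls, so it does not settle the matter.

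A reader might also infer that controls are followed for the whole study period, which with "DURATION OF ACCRUAL: 24 months" and 9 months of follow-up would be about 33 months. Section 1.3.3 puts the difference between the two groups within 9 months of follow-up, and *during the study period* reads more naturally as calendar concurrency. The intended length is therefore 9 months in both groups. Nor would a long control window by itself cost power in the planned primary analysis: section 1.3.3 assigns that outcome to log-rank, Cox and Kaplan-Meier methods, and a Kaplan-Meier proportion can be read at 9 months. The missing start date and the inapplicable censoring rule stand.

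On waiting time, adjustment for significant stratifying variables could admit it, and no imbalance has been shown. Both are fair. But an unnamed covariate, admitted according to its significance, is not pre-specified control of a factor known at the design stage to govern entry.

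**Conclusion.** The point holds, and the wording should be changed before control data are drawn. The main weakness is possible confounding by waiting time: it governs entry to the treated group and appears in no matching or named adjustment rule. Its size and direction are unknown. The table above rests on assumed hazard ratios and constant hazard, and shows only how far the effect estimate depends on the omitted factor. It would go too far to say that the comparison is shown to be biased, or that it must favour treatment.

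The selection phrase, time zero and censoring rule are definitional gaps. The intent (control transplants counted, 9 months in both groups) can be recovered from the text, but a workable specification cannot.

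The point covers only the concurrent comparison. It does not cover the confidence-interval comparison with historical UNOS rates in section 1.2, or the different primary end point under Study Objectives. Confidence is moderate, because Appendix A, section 2.0, section 9.0 and the UNOS tables are not in the supplied text and could define the controls further.

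**What to change.** Amend sections 1.1 and 1.3.3 as follows.

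- **Selection.** Choose controls who are active on the UNOS list at an index date. Keep them whatever their later outcome, and count their transplants as events.
- **Time zero.** Use a rule that also covers treated patients who do not complete treatment, as intention-to-treat requires. It could be the start of treatment, or its scheduled completion date, with the same calendar date for the matched controls. Actual completion would leave non-completers and their controls without a start date. Align the end-point wording in section 1.3.1 with the choice.
- **Window and censoring.** Use the same 9 months from the index date and the same censoring rule in both groups, stated without reference to desensitization.
- **Waiting time.** Match on accrued waiting time at the index date in addition to age and cPRA, or pre-specify it as a covariate in the primary Cox model. Name the remaining covariates and drop selection by significance.

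The cost is SAP text and a larger registry request; no patients or procedures are added. Some treated patients will have fewer matches, and the apparent effect may be smaller.

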DATA SAFETY MONITORING A major component of this study will be to determine the safety of this combination of drugs for desensitization and subsequent transplantation. In order to insure this is done, a Data Safety Monitoring Board ([name], [name] (Bone Marrow Transplantation) & Vo) will be created to monitor AEs and SAEs that occur during the study. Cedars-Sinai will maintain the database for all patients entered into the study and will be responsible for accumulation of safety data and reporting to participating centers and Genentech with each occurrence.

RECIPIENT INCLUSION CRITERIA:

1. End-stage renal disease.
2. No known contraindications for therapy with IGIV10%/Rituximab.
3. Age 18-70 years at the time of screening.
4. CPRA \geq 30% demonstrated on 3 consecutive samples, UNOS wait time sufficient to allow DD offers, history of sensitizing events, positive crossmatch with the intended donor.
5. Subject/Parent/Guardian must be able to understand and provide informed consent.

RECIPIENT EXCLUSION CRITERIA:

1. Lactating or pregnant females.
2. Pediatric patients <18 years of age
3. Women of child-bearing age who are not willing or able to practice FDA-approved forms of contraception.
4. HIV-positive subjects.
5. Subjects who test positive for HBV infection [positive HBsAg, HBcAg, or

HBVeAg/DNA] or HCV infection [positive Anti-HCV (EIA) and confirmatory HCV RIBA].

6. Subjects with active TB.
7. Subjects with selective IgA deficiency, those who have known anti-IgA antibodies, and those with a history of anaphylaxis or severe systemic responses to any part of the clinical trial material.
8. Subjects for whom multiple organ transplants are planned.
9. Recent recipients of any licensed or investigational live attenuated vaccine(s) within two months of the screening visit (including but not limited to any of the following:
 - Adenovirus [Adenovirus vaccine live oral type 7]*
 - Varicella [Varivax]*
 - Hepatitis A [VAQTA]*
 - Rotavirus [Rotashield]*
 - Yellow fever [Y-F-Vax]*
 - Measles and mumps [Measles and mumps virus vaccine live]*
 - Measles, mumps, and rubella vaccine [M-M-R-II]*
 - Sabin oral polio vaccine*
 - Rabies vaccines [IMOVAX Rabies I.D., RabAvert]*
10. A significantly abnormal general serum screening lab result defined as a WBC < 3.0 X 10³/ml, a Hgb < 8.0 g/dL, a platelet count < 100 X 10³/ml, , an SGOT > 5X upper limit of normal, and an SGPT > 5X upper limit of normal range.
11. Individuals deemed unable to comply with the protocol.

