If the 9-month transplant rate is 50% (or 60 to 65%) then the 12-month rate should be even higher. During the placebo controlled phase of this study, the 13/15 patients were transplanted at a mean of 7 months post treatment. (7 IVIG + Placebo v. 6 IVIG + Rituximab). The mean wait time on dialysis for this group was > 11 years prior to being entered into the study and transplanted. Our original time of assessment of transplantation

was 6M. However, with this preliminary data, we felt it better to look at 9M since this would likely be more reasonable and would give a fair assessment of the efficacy of the therapy. We feel we are being conservative with these estimates. Hopefully, this clarifies the sample size calculation issues.

Column 1: the lower limit of the CI is 0.373 or about 37% when the sample size is 60.

Column 2: the lower limit of the CI is 0.383 or about 38% when the sample size is 70.

Column 3: the lower limit of the CI is 0.387 or about 39% when the sample size is 75.

If the upper limit of the UNOS CI (historical data) is below the lower limit of the above CI, then the CI do not overlap and there is evidence that IVIG + Rituximab is more effective re the 12-month transplant rate.

Given the UNOS data for transplant rates (Table 4 & 5), 60 should be sufficient as a sample size to show benefit of the IVIG + Rituximab treatment. However, 75 patients gives a better and more robust distinction. Since we will be looking at transplant rates at 9M post-treatment, and given the vagueness of organ allocation and patient readiness issues, we feel the choice of 75 patients will provide more security for an accurate and definitive study.

If the observed 12-month IVIG + Rituximab transplant rate is > 50%, then the effectiveness evidence is even stronger (the lower limit of the CI will be higher).

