1.3.1 Primary Efficacy Variables

The primary efficacy variable is the number of highly-HLA sensitized patients receiving a deceased donor transplant within 9 months after completion of the treatment. From our previous experience, the anticipated transplant rates for patients receiving IVIG + Rituximab desensitization is ~70% (49,112, 131). The rates for DD transplantation in non-treated patients based on sensitization levels is shown in Figure 15 below. Briefly, the rates of transplantation for all sensitized patients are <12% per year for the past decade. This indicates that desensitization

with IVIG + Rituximab is likely to benefit this high risk group who are otherwise unlikely to receive a life-saving transplant.

[figure not shown]

Figure 15: Data shown in figure 14 represent an analysis of 95,083 deceased donor transplants performed over the 10 year period 2000-2009. When analyzed by PRA status, one can see that <20% of all transplants performed are in highly-HLA sensitized patients. Data from the United States Renal Data Systems (usrds.gov) for 2009 also show that the wait time for a deceased donor kidney for patients with PRAs <10% is 4 years but increases to 8 years for patients with PRAs >10%. These trends have not changed over the past decade.

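### UNOS controls are chosen on age and anti-HLA antibody alone, without the trial's eligibility criteria, so the primary comparison is open to confounding by eligibility

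*Combined protocol and SAP*

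**What the plan says.** Section 1.1 (Primary Objective) makes the transplant rate over 9 months after treatment the primary end point and compares it with that of "age and anti-HLA antibody matched patients who remain on the UNOS wait list during the study period". The stated conditions are an age match, an antibody match and a place on the list.

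The same section plans on a control rate of about "15% in the non-desensitized patients on UNOS wait list". Section 1.3.1 describes its background data in similar terms: "The rates for DD transplantation in non-treated patients based on sensitization levels is shown in Figure 15 below".

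Treated patients face a longer list. The Recipient Inclusion Criteria ask for CPRA of at least 30% on three consecutive samples, waiting time long enough to draw deceased-donor offers, a history of sensitizing events and a positive crossmatch. The Recipient Exclusion Criteria remove, among others, patients with HIV, HBV, HCV or active TB, active CMV or EBV, abnormal screening laboratory values, myocardial infarction within a year, significant thrombosis or active peripheral vascular disease, expected non-compliance, and "Subjects for whom multiple organ transplants are planned".

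Section 1.3.3 compares the treated group with the UNOS control group by log-rank test and unadjusted Cox hazard ratios. It adjusts for stratifying variables that prove significant. The only one it names is PRA above or below 80%. It derives the number needed to desensitize from the hazard ratio and reports absolute risk differences as well.

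**The concern.** Without randomisation, the comparison is only as good as the rule that picks the controls. Treated patients are screened on several features that plausibly bear on whether a candidate gets and accepts a kidney. Controls, by the written rule, are not. A control could be inactive on the list, listed for more than one organ, too recently listed to receive offers, or excluded from the trial on infectious or cardiovascular grounds.

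If such candidates are transplanted less often, the control rate is too low for the question asked, and part of the apparent benefit belongs to screening. The error would run in the same direction through the hazard ratio, the risk difference and the number needed to desensitize.

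The analysis does not remove it. Fitness and active listing are neither matched nor named for adjustment, and the one named stratifier, PRA, overlaps with the antibody match. More patients would narrow the interval but leave the bias where it is.

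**Working it through.** **Inputs**

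- Treated 9-month rate pT = 65%. This is the top of "60-65% in the IVIG + Rituximab group" in 1.1, and it fits the difference of "approximately 50 percentage points between the two groups during 9 months of follow-up" in 1.3.3.
- Control rate pC = 15% (1.1 and 1.3.3).
- Share f of controls who would fail the trial's criteria: not in the documents. Assumed 10%, 20% and 30%.
- Transplant rate of ineligible controls as a fraction k of the rate in eligible controls: not in the documents. k = 0 is the extreme case.
- Number of controls: not stated. 75 is assumed for power.

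**Step 1. The plan's own effect.** The risk difference is 65 − 15 = 50 points, as 1.3.3 states. Under proportional hazards, HR = ln(1 − pT)/ln(1 − pC) = ln 0.35/ln 0.85 = 1.0498/0.1625 = 6.46.

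On power, 65% versus 15% at two-sided 5% needs 22 per group for 95% power, or 25 after 10% loss. With 75 per group, power is above 99.9%. The stated 95% is therefore not reproduced, but the gap is on the safe side and this point does not depend on it.

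**Step 2. Rate among eligible controls.** If the 15% is the rate in the mixed pool, then pC = (1 − f)·pE + f·k·pE, so pE = pC/(1 − f(1 − k)). With k = 1 there is no shift. With k = 0, pE = 0.15/(1 − f), the largest shift for a given f if ineligible controls are transplanted no more often than eligible ones.

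**Step 3. Effect against eligible controls, k = 0.** HR = ln 0.35/ln(1 − pE). Risk difference = 0.65 − pE. Number needed to desensitize = 1/[(1 − pE) − (1 − pE)^HR]. Because (1 − pE)^HR = 0.35, this equals 1/(0.65 − pE).

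| f | pE | HR | Risk difference (points) | Number needed |
|---|---|---|---|---|
| 0 | 15.0% | 6.46 | 50.0 | 2.0 |
| 10% | 16.7% | 5.76 | 48.3 | 2.1 |
| 20% | 18.8% | 5.06 | 46.2 | 2.2 |
| 30% | 21.4% | 4.35 | 43.6 | 2.3 |

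**Step 4. Does significance survive?** With 75 per group, power against these eligible-control rates stays above 99.9% at pT = 65%. At pT = 50%, the rate used for precision in 1.2, the HR goes from 4.27 to 3.80, 3.34 and 2.87 for f = 10%, 20% and 30%. Power is then 99.4%, 98.6% and 96.2%. The test is not threatened at the planned effects.

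**The case against.** - **Ineligible is not the same as untransplantable.** Several exclusions concern the study drugs or trial conduct (IgA deficiency, recent live vaccine, contraception, recent investigational agents). No section says that listed candidates with viral infection or multi-organ plans go without a kidney. This stands. The direction of the bias is conditional, k = 0 is an extreme, and the table illustrates a mechanism without estimating the bias.
- **The controls are meant to be untreated.** A reader might infer that the comparator contains desensitized patients in number. The documents do not support that: 1.1 and 1.3.1 describe the comparison patients as non-desensitized and non-treated, 1.3.3 treats the two groups as separate, and no figure suggests contamination. What remains is narrower. The description appears as a rate assumption and as background, not as a selection rule, and no exclusion covers this trial's own patients.
- **Patient readiness.** A reader might take "given the vagueness of organ allocation and patient readiness issues" in 1.2 as an admission that controls differ in fitness. There it only supports choosing 75 rather than 60 treated patients.
- **Which effect measure.** The plan does not rank the hazard ratio above the risk difference. The primary variable in 1.3.1 is a number transplanted, the sample size in 1.3.3 is argued in percentage points, and both measures are to be reported. On the absolute scale the illustrated shift is 1.7-6.4 points out of 50.
- **Exploratory study, robust conclusion.** This is an open-label Phase I/II study and significance would hold. That is correct, and it limits the weight of the point.
- **Missing material.** Section 2.0, section 9.0, Appendix A and Tables 4 and 5 are referred to but are not in the text available. Control selection could be detailed there. If so, 1.1 and 1.3.3 should point to it.

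**Conclusion.** The concern holds in a limited form. The written control rule omits eligibility criteria that treated patients must meet, and nothing in the available analysis plan compensates. The comparison is therefore open to confounding by eligibility, in favour of treatment to the extent that ineligible or inactive candidates are transplanted less often.

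The size cannot be known from the documents. The illustrated hazard ratios and risk differences rest on assumed shares and on no transplants at all among ineligible controls, so for each share they bound the shift from above.

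A reader might go further and infer that the trial's conclusion is unsafe. The figures do not show that: at the planned effect the difference remains large and significant. What suffers is the size and interpretation of the effect estimate and of the number needed to desensitize, which matter because this comparison is the trial's evidence on efficacy. The plan should be changed before control data are extracted, so that the filters cannot be chosen in the light of the results.

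**What to change.** In 1.1 and 1.3.3:

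1. Define an index date for each control. Require the control to meet, on that date, every trial eligibility criterion that bears on transplantability and that the UNOS record carries. Examples are kidney-alone listing, the same age and CPRA limits, able to receive offers, and waiting time long enough to draw them.
2. Exclude anyone enrolled in this trial or its placebo-controlled phase, and anyone known to have been desensitized. This turns the existing description into a rule.
3. List the criteria that the registry cannot verify, and state residual confounding as a limitation of the primary comparison.

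Before the filter is written, the age limits need reconciling: Target Population gives 18-65 years and the inclusion criteria give 18-70.

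The cost is plan wording and a filter on the registry extract. The control pool will be smaller, and some clinical exclusions will stay unverified. The documents do not say which fields the UNOS record holds, so this must be checked first. Nothing changes for enrolled patients.
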